## SCHEMA

- Patients with rectal adenocarcinoma either locally advanced or metastatic rectal adenocarcinoma requiring chemoradiation to the primary lesion are eligible.
- Patients with locally advanced rectal adenocarcinoma (T3 or T4, at risk of having a positive surgical radial margin and/or N+), or patients with metastatic disease requiring chemoradiation.
- Patients will be treated with FOLFOX chemotherapy x 4 doses over 8 weeks (weeks 1-8) followed by short course radiation over 5 days (weeks 9 or 10).
- Subsequently, starting approximately 2 weeks after finishing short course RT, patients will receive FOLFOX chemotherapy x 4 doses (weeks 12 / 13 – 19 / 20). While surgical resection of the primary is not mandatory, those requiring surgery will undergo resection 8-16 weeks later (weeks 27 - 36) and / or further systemic therapy per treating physician's discretion.
- Talimogene laherparepvec will be administered via endoscopy by a qualified physician for a total of 4 doses at the following time points: a) week prior to c1 FOLFOX b) weeks 3, 5 and 7 during FOLFOX
- Dose escalation will be done using a 3 + 3 design over 2 cohorts and a total of 15 patients

Dose level+	TALIMOGENE LAHERPAREPVEC Dose (PFU/ml)	Capecitabine (mg/m  po bid on days of radiation)	Radiation	Comments
1	1x 10  , 1x 10  , 1x 10  , 1x 10 	825	50.4 Gray in 28 fractions	Completed prior to protocol amendment 1/23/21
1 (amended)	1x 10  , 1x 10  , 1x 10  , 1x 10 	N/A	25 Gray in 5 fractions	To be implemented if DLTs noted with DL 2
2	1x 10  , 1x 10  , 1x 10  , 1x 10 	N/A	25 Gray in 5 fractions	

will be treated at MTD.

Dose limiting toxicities (DLTs) will be captured until completion of FOLFOX chemotherapy (weeks 18/9) and will be graded according to the CTCAE ver 5.0.

#Patients with inadequate archival tissue for integrated biomarker analysis

^As part of pre-surgical evaluation or at a corresponding time point in patients not undergoing surgery

+Dose escalation will be done using a 3+3 design for a total of 15 patients that will be treated at MTD

TVEC = talimogene laherparepvec

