#### Summary of specimen requirements:

Time Point	Specimen and Quantity	Send Specimens to:
Archival Specimens		
	• 2 FFPE tissue cores 	ETCTN Biorepository
Baseline		

	

• 2 FFPE tissue cores

• 1-2 tissue cores snap-frozen

• 20 mL blood in green-top Na-Hep tube

• 10 mL blood in cfDNA Streck tube

	ETCTN Biorepository
	

• 2 mL EDTA whole blood

	ETCTN Biorepository
Week 7		
	

• 2 FFPE tissue cores

• 1-2 tissue cores snap-frozen

• 10 mL blood in cfDNA Streck tube

	ETCTN Biorepository
	

• 20 mL blood in green-top NaHep tube

	ETCTN Biorepository
Week 30-35		
	

• 2 FFPE tissue cores

• 1-2 tissue cores snap-frozen

• 10 mL blood in cfDNA Streck tube

	ETCTN Biorepository
	

• 20 mL blood in green-top NaHep tube

	ETCTN Biorepository

A copy of the radiology and operative reports from the tissue removal procedure must be sent with the tissue to the ETCTN Biorepository. When completed, upload the corresponding pathology reports to Rave.

This may be collected at a later time point for patients already on-study.

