#### 9.2.1 Biopsy Collection Procedure (Formalin Kits)-Cores #1 And #2

Up to four core biopsies at least 1 cm in length will be obtained (if possible). Biopsies will be sent for analyses as defined in the protocol.

Note: Two cores (#1-2) biopsies will be fixed in formalin and placed in 70% Ethanol. Additional cores (#3) and (#4) will be immediately snap- frozen in vapor phase of Liquid Nitrogen (LN2) (see instructions below). If more than four biopsies are obtained, then additional biopsies will be collected in formalin and sent to the biorepository in 70% Ethanol for embedding. Kits are supplied by the ETCTN Biorepository only for specimens shipped to the Biorepository by the ETCTN Biorepository at Nationwide Children's Hospital. Kits should be ordered before specimen collection.

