### 9.2.3 Whole Blood

#### Whole blood collection in green-top tubes

- 1) Label 10-20 ml green-top (NaHep) tubes, Becton Dickinson Cat No. 367874 or equivalent, with Rave generated specimen ID (which includes the protocol number and Universal Patient ID), an Intrinsic ID, specimen type (blood), and collection date.
- 2) Collect 10-20 ml of peripheral blood in 10ml green-top (NaHep) tubes. **Collect 20 mL at Baseline, and 10 mL at Week 8 and Week 21-25.**
- 3) After collection, gently invert tube(s) 5-10 times to ensure adequate mixing of sodium heparin. Maintain specimens at ambient temperature (room temperature) during collection and transport.
- 4) **All green top tubes (or 10 mL of blood) will be shipped to the ETCTN Biorepository.**
- 5) See section 9.5 for instructions for shipping to the ETCTN Biorepository at Nationwide Children's Hospital.

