#### Collection in cfDNA Streck tubes:

- 1) Label one 10 mL cfDNA Streck tube, with Rave generated specimen ID (which includes the protocol number and Universal Patient ID), an Intrinsic ID, specimen type (blood), and collection date.
- 2) At all-time points, collect 10 ml of blood into the pre-labeled tube and invert to mix. **Note: blood must be thoroughly mixed to ensure preservation of specimen.**
- 3) After collection, blood in cfDNA Streck tubes **should never be refrigerated**, as this will compromise the specimen. Blood collected in cfDNA Streck tubes is stable at room temperature.

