## 9.4 Shipping of Biospecimens from Clinical Sites to the ETCTN Biorepository

### Shipping of Specimen(s):

**Ambient temperature shipments:** include core biopsies in formalin, blood in cfDNA Streck tube, and blood in green-top tubes (at Baseline only) in one shipment to the Biorepository on Monday through Wednesday, using the same box to ship that was used to receive the kit contents. Note: If blood is collected on Wednesday through Friday then it may be shipped separately from the tissue, on the day of collection.

- Place specimens (separated by specimen type) in zip-lock bags.
- Place zip-lock bags in a biohazard envelope containing absorbent materials. Next, place the biohazard envelope into a Tyvek envelope. Expel as much air as possible before sealing each envelope.
- Place the Tyvek envelope into the shipping container. In warm months, place a cold (NOT frozen) gel pack into the container with the specimens.
- Insert a copy of the shipping manifest and any other required paperwork, including operative and radiology, and/or pathology reports, into the container with the specimens. Place paperwork in a plastic zip-lock bag to prevent potential contamination in case of specimen leakage.
- Place the cover on the shipping container. Tape the shipping container closed with durable tape.
- Attach the FedEx air bill and attach to top of shipping container.
- Attach an Exempt Human Specimen sticker to the side of the shipping container.
- Make arrangements for courier pickup.

**Frozen shipments:** Serum (four aliquots) and snap-frozen core biopsies may be combined as one shipment on dry ice to the biorepository. Ensure that sufficient dry ice is included to completely encase the specimens to maintain specimen integrity during shipment. Frozen specimens may be shipped on Monday through Thursday.

Pre-fill the shipping container about 1/3 full with dry ice.

Place specimens (separated by specimen type) in zip-lock bags.

Place zip-lock bags in a biohazard envelope containing absorbent materials. Next, place the biohazard envelope into a Tyvek envelope. Expel as much air as possible before sealing each envelope.

Place the Tyvek envelope into the shipping container and fill the container to the top with additional dry ice.

Insert a copy of the shipping manifest and any other required paperwork, such as a pathology report, into the container with the specimens. Place paperwork in a plastic zip-lock bag in case of sample leakage.

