### 13.4 Analysis of Secondary Endpoints

Secondary objectives of the study include determining feasibility and NAR.. Feasibility will be reported in all patients who have started therapy as percent of planned dose intensity, NAR will be reported in all patients who undergo resection. NAR will be calculated as detailed in section 2.6 and will be reported using descriptive statistics. pCR will be reported with proportions along with the appropriate confidence intervals and survival by Kaplan-Meier method. Descriptive statistics will be used to report results of other correlative studies discussed above. Tumors will

be characterized into good and poor responders to enable binary comparison. mrTRG is based on similar principles to the pathologic TRG and is based on the degree of tumor replaced by fibrotic stroma on post-treatment pelvic MRI. mrTRG-5 (no fibrosis, only tumor signal visible), mrTRG4 (predominantly tumor signal with minimal fibrotic stroma) will be defined as poor responders whereas mrTRG-1 (no tumor signal) to mrTRG-3 (50% or greater fibrotic stroma) will be defined as good. For the purposes of CRM, a margin greater than or equal to 1 mm between the tumor and the resection margin will be defined as clear (good responder) and the rest as poor responders. Prognosis of good responders including DFS, OS and local recurrence will be compared to that of poor responders. Furthermore, mrTRG will be compared to histological TRG (ypTRG) to validate its accuracy. Two radiologists with extensive experience with rectal MRIs (Drs. [name] & [name]) will read all the scans to minimize inter-observer variability.

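### Section 9 gives two incompatible schedules for the green-top flow-cytometry blood, and one of them puts the last draw inside the surgery window

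*Combined protocol and SAP*

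**What the plan says.** Four places in the combined protocol and SAP bear on this blood sample.

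- **Section 9.1, specimen table.** Baseline lists "20 mL blood in green-top Na-Hep tube". The Week 7 and Week 30-35 rows list the same tube and the same 20 mL. The Week 30-35 row also lists two fixed and one to two frozen tissue cores. It does not state whether sampling comes before or after surgery.
- **Section 9.2.3, green-top procedure.** The instruction is "Collect 20 mL at Baseline, and 10 mL at Week 8 and Week 21-25". A later step adds: "All green top tubes (or 10 mL of blood) will be shipped to the ETCTN Biorepository".
- **Section 9.4, shipping.** The ambient shipment includes "blood in green-top tubes (at Baseline only"; green-top tubes from later visits are not mentioned by name.
- **Section 10, calendar.** Note l sends the reader back to Section 9 for tube types and volumes. Notes i and n make biopsies optional and surgery non-mandatory.

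On surgery, the Schema says "those requiring surgery will undergo resection 8-16 weeks later (weeks 27 - 36" after the second FOLFOX block, and Section 10 allows two weeks either side. Section 10 places the pre-surgical tumour measurements and imaging at weeks 21-25.

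The blood serves objective 1.3.2 (immune-cell proportions in serial samples), the peripheral T-cell part of hypothesis 2.6.4, and Section 9.9.5 (flow cytometry). Section 13.4 says of the analysis: "Descriptive statistics will be used to report results of other correlative studies discussed above".

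**The concern.** Two current instructions for the same tube disagree on the week of both post-baseline draws and on the volume of each, and the calendar does not settle the matter. Sites, or staff within one site, may follow different sections. What is then reported as one on-treatment and one post-treatment sample would combine draws from different points in the regimen.

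The last draw matters most. Under the specimen table it falls in the weeks when resections take place. Blood taken before and after major surgery does not represent the same state, so a change from baseline that pools the two would partly reflect the operation. A patient already resected also has no primary tumour left for the optional cores in that row.

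The stake is the readability of a small exploratory comparison: 15 patients at the MTD (Section 13.1) and no more than 21 overall (Section 13.2). A few samples in a different surgical state could shift a descriptive summary, and a mistimed draw cannot be repeated.

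**Working it through.** **1. The two schedules side by side**

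| Draw | Section 9.1 table | Section 9.2.3 | Difference |
|---|---|---|---|
| Baseline | 20 mL | 20 mL | none |
| On treatment | Week 7, 20 mL | Week 8, 10 mL | 1 week, 10 mL |
| Last | Week 30-35, 20 mL | Week 21-25, 10 mL | see step 2 |
| Total | 20 + 20 + 20 = 60 mL | 20 + 10 + 10 = 40 mL | 20 mL, or 20/60 = 33% |

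Week 7 is the week of the fourth talimogene laherparepvec injection (Schema; Section 5.1). Week 8 is one week later.

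**2. Gap between the two last draws**

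Smallest: 30 − 25 = 5 weeks. Largest: 35 − 21 = 14 weeks. The windows do not overlap.

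**3. The plan's surgery window, reproduced**

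The Schema's second FOLFOX block ends at week 19/20, and resection follows 8-16 weeks later. 19 + 8 = 27 and 20 + 16 = 36, which matches the stated weeks 27-36. Counting from the last doses at weeks 18/19 in Section 5.1 would give 26-35, so the stated window runs from 19/20. With the two-week allowance in Section 10 it becomes 25-38.

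**4. Overlap of sampling and surgery**

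- Week 30-35: all 6 sampling weeks lie within 27-36.
- Week 21-25: no overlap with 27-36; only week 25 touches 25-38.

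Under the Week 30-35 label, a patient resected in weeks 27-29 can only be sampled after surgery, and one resected in week 36 only before it. For resections in weeks 30-35 the order depends on the days chosen.

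**5. Possible size of the mix**

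The documents give no distribution of surgery dates. As an assumption, take surgery uniform over the 10 weeks 27-36 and sampling uniform and independent over the 6 weeks 30-35, giving 10 × 6 = 60 equally likely pairs.

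- Surgery in an earlier week than the sample: 3 + 4 + 5 + 6 + 7 + 8 = 33, and 33/60 = 55%.
- Same week: 6/60 = 10%.
- Surgery in a later week: 60 − 33 − 6 = 21, and 21/60 = 35%.

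With surgery uniform over the 14 weeks 25-38 there are 14 × 6 = 84 pairs, and (5 + 6 + 7 + 8 + 9 + 10)/84 = 45/84 = 54% are post-operative. If every site ties the draw to the pre-surgical evaluation, the figure is 0%.

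**6. What does not conflict**

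For the cfDNA tubes Section 9.2.3 says "At all-time points, collect 10 ml of blood into the pre-labeled tube and invert to mix", which matches the table. For tissue, Section 9.2.1 says "Up to four core biopsies at least 1 cm in length will be obtained (if possible", which fits two fixed plus one to two frozen cores.

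**The case against.** **The protocol may already intend a pre-operative sample.** A Schema footnote speaks of pre-surgical evaluation, with a corresponding time point for patients not having surgery. A reader might infer that it governs this draw, so that no mixing is planned. The footnote's anchor is not visible in the text available, so the link is plausible but not established, and the Week 30-35 row itself carries no such condition. It does rule out saying that samples *will* be mixed; they *can* be.

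**The biopsy schedule.** A reader might infer that biopsy weeks and quantities also contradict each other. The documents do not show this. Core numbers agree, Section 9.2.3 concerns blood only, and the table in Section 9.1 is the only legible source of biopsy weeks. The calendar's column alignment was lost in extraction, and parts of Section 9 are not available. For tissue, the surgery overlap mainly means possible missing optional cores. The green-top conflict does not touch the PD-L1 hypothesis in Section 2.6.3, which uses tumour biopsies.

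**Shipping.** The baseline-only phrase in Section 9.4 could be read as saying later tubes are never sent. It sits in a description of one combined blood-and-tissue box, a note there permits separate blood shipments, and Section 9.2.3 ships all green-top tubes. It is ambiguous and needs clarifying.

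**Safeguards and importance.** Section 9.3 already requires the collection date and time of every sample, so analysis by actual date is possible. Section 9.1 defers decisions on processing these tubes until a laboratory is chosen, but does not defer collection weeks or volumes. The endpoint is exploratory and measures proportions of cells, and no effect of draw volume on proportions is shown. These points stand, and they keep the matter minor.

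**Conclusion.** The point holds as an internal inconsistency of minor weight. The green-top schedules in Sections 9.1 and 9.2.3 cannot both be followed: they differ by one week on treatment, by 5 to 14 weeks at the last draw, and two-fold in each post-baseline volume. The Week 30-35 draw lies entirely within the stated surgery window, with no instruction to sample first.

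The post-operative share among resected patients is 0% if sampling is tied to pre-surgical work-up, and about 55% under uniform, independent timing. The second figure is an illustration that rests on that assumption, not a ceiling or a forecast. Surgery is optional, so the question arises only in patients who are resected.

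A reader might take 15 as the maximum number of patients with paired samples. The documents give 15 as the MTD group and 21 as the accrual limit; they state no number with paired blood.

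The effect is confined to the descriptive peripheral immune-cell comparison (objective 1.3.2, hypothesis 2.6.4). Nothing here bears on DLT assessment, the MTD or the NAR score.

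**What to change.** 1. Replace the instructions in Sections 9.1, 9.2.3 and 9.4 and the blood row of Section 10 with one table of weeks and volumes, or with references to it. State there how green-top tubes collected after baseline are shipped.
2. Tie the last on-study sample to the pre-surgical evaluation, and define a corresponding time point for patients who are not resected.
3. In Section 13.4, say that the pre- to post-treatment change is reported from pre-operative samples, classified by the collection date already recorded under Section 9.3 against the surgery date. Report post-operative and post-progression samples separately. Dropping every post-operative sample would be too broad: objective 1.3.2 names a post-progression sample, which in a resected patient comes after surgery. Neither Section 9 schedule contains that sample, so the objective and the table should also be aligned.

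The cost is wording in these sections. No extra sample is needed, and nothing changes in dose escalation or the primary analysis.

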#### Collection in cfDNA Streck tubes:

- 1) Label one 10 mL cfDNA Streck tube, with Rave generated specimen ID (which includes the protocol number and Universal Patient ID), an Intrinsic ID, specimen type (blood), and collection date.
- 2) At all-time points, collect 10 ml of blood into the pre-labeled tube and invert to mix. **Note: blood must be thoroughly mixed to ensure preservation of specimen.**
- 3) After collection, blood in cfDNA Streck tubes **should never be refrigerated**, as this will compromise the specimen. Blood collected in cfDNA Streck tubes is stable at room temperature.

#### Whole blood collection in K2 EDTA purple-top tubes

- 1) Collect 2 mL of peripheral blood into a labeled K2 EDTA Purple-Top Tube; each tube must be filled completely to ensure the correct blood/anticoagulant ratio.

- 2) After collection, gently invert tube(s) 8-10 times to ensure adequate mixing of EDTA. Maintain specimens at ambient temperature (room temperature) during collection and transport.
- 3) See section 4.0 for instructions for shipping to the ETCTN Biorepository at Nationwide Children's Hospital.

An external sample label should be fixed to the shipping container to alert the Biorepository of **blood** sample collection **time** and **date** (this helps to identify and prioritize received samples that have processing time requirements).

Blood should be shipped ambient FedEx Priority Overnight to the biorepository where it is processed the day of receipt **within 24 hours of collection (not to exceed 48 hours)**.

### 9.3 Sample Tracking System Instructions

All biospecimens collected for this trial must be submitted using the ETCTN Rave Specimen Tracking System (STS) unless otherwise noted. The system is accessed through special Rave user roles: “CRA Specimen Tracking” for data entry at the treating institutions and “Biorepository” for users receiving the specimens for processing and storage at reference labs and the Biorepository. Please refer to the Medidata Account Activation and Study Invitation Acceptance link on the CTSU website under the Rave/DQP tab.

**Important: Failure to complete required fields in STS may result in a delay in sample processing.** Any case reimbursements associated with sample submissions will not be credited if samples requiring STS submission are not logged into STS.

Additionally, please note that the STS software creates pop-up windows when reports are generated, so you will need to enable pop-ups within your web browser while using the software.

For questions regarding the Specimen Tracking System, please contact the Theradex Help Desk at [[contact]](mailto:[contact]).

A shipping manifest **must** be included with all sample submissions.

#### Pre-Analytic Information

Collection site must record all preanalytical information and enter the following into a specimen tracking system (STS) used by each trial network or record and provide with shipping manifest:

- 1) Time/date blood or tissue sample collection was made as ***Time/Date Specimen Collected***.
- 2) Ischemia start time (time when sample was devascularized OR estimated time of surgery)—***Tissue Collection Time/Date***.
- 3) Ischemic end time ***for each tissue core and surgical segment*** (time when sample was moved to preservative such as formalin or dry ice)—***Tissue Processing (Formalin Start) Time/Date***.
- 4) Completion of formalin fixation should be recorded as ***Formalin End Time/Date*** in the STS (or under “comments” if field is not available).
- 5) Start of 70% Ethanol dehydration should be recorded as ***Ethanol Start Time/Date*** in STS (or under “comments” if field is not available)
- 6) Time when fixed tissue, held in Ethanol, was placed into an automated processor should be recorded as ***Ethanol End Time/Date*** in the STS (or under “comments” if field is not available).
- 7) Core # for each core needle biopsy obtained. Each core should be recorded in the STS as a separate specimen with a unique Specimen ID that captures the chronological order in which the biopsy cores were obtained.

Biorepository will collect the following information for received specimens:

- 1) Date of sample receipt.
- 2) Time/date formalin-fixed tissue in Ethanol is moved into an automated processor—***recorded as Ethanol End Time***.
- 3) Record if frozen tissue sample arrived with insufficient amount of dry ice.
- 4) Collected pre-analytic information will be entered into the shipping manifest (NCI specimen tracking system).

### **9.3.1 Specimen Labeling**

#### **9.3.2.1 Blood Specimen Labels**

Include the following on blood specimens (including whole blood and frozen, processed blood products – like serum and plasma):

- Patient study ID
- Universal Patient ID (UPID)
- Specimen ID (automatically generated by Rave)
- Time point
- Specimen type (e.g. blood, serum)
- Collection date (to be added by hand)

#### **9.3.2.2 Tissue Specimen Labels**

Include the following on all tissue specimens or containers (e.g. formalin jar).

- Patient study ID

- Universal Patient ID (UPID)
- Specimen ID (automatically generated by Rave)
- Time point
- Specimen type (e.g. FFPE Block, Formalin Fixed Tissue, Fresh Tissue in Media, etc.)
- Tissue type (P for primary or M for metastatic, and B for baseline, I for Injected, AND U FOR Uninjected)
- Surgical pathology ID (SPID) number
- Block number from the corresponding pathology report (archival only)
- Collection date (to be added by hand)

